5.4.2.2 Pomalidomide Dose Modifications for Specific Toxicities

Table 4 Pomalidomide Dose Modification for Hematologic Toxicity

Toxicity	Action / Considerations
Delay of >2 weeks due to cytopenias, per Criteria for Initiating a New Cycle of Treatment.	
 • If event is solely neutropenia, consider adding G-CSF and resuming at prior dose of pomalidomide. • For all other events, upon count recovery, reduce pomalidomide by one dose level.
Mid-cycle grade 4 thrombocytopenia (platelets < 25 × 10 ⁹ /L)	
 • Hold pomalidomide and continue other study therapies if clinically appropriate. • Consider holding VTE prophylaxis (aspirin or anticoagulation) if subject is currently taking it.

	
 Resume pomalidomide with one dose level reduction only when the subject's platelets recover to $\geq 50 \times 10^9/L$
Mid-cycle grade 4 neutropenia ($ANC < 0.5 \times 10^9/L$) OR any grade febrile neutropenia	
 Hold pomalidomide and continue other study therapies if event is not febrile neutropenia and continuing is felt to be clinically appropriate. Resume pomalidomide when ANC recovers to $\geq 1 \times 10^9/L$ and fever and/or infections, if present, have resolved. If investigator plans on adding G-CSF and no other indication for reducing study therapies exists, may resume pomalidomide at same dose. If subject was already on short-acting G-CSF ≥ 3 times weekly (e.g., Neupogen or Granix) or long-acting G-CSF at any frequency (e.g., Neulasta), OR investigator does not feel G-CSF is clinically appropriate, reduce pomalidomide one dose level. For each subsequent drop of ANC less than 0.5×10^9, pomalidomide will be held and other study therapies will continue if continuation is felt to be clinically appropriate. Pomalidomide will then resume with one dose-level reduction when ANC recovers to $\geq 0.5 \times 10^9/L$.

Table 5. Other Treatment Modifications/Delays for Non-Hematologic Toxicity

Adverse Event (Severity)	Action on Study Drugs	Further Considerations
GI Grade ≥ 2 diarrhea	
 • Ensure supportive care (anti-motility agents, bile acid sequestrants, etc.) are maximized. • If diarrhea is attributed to pomalidomide, hold pomalidomide until resolution to Grade ≤ 1. • If event occurred without maximal supportive care (per discretion of the treating clinician), resume pomalidomide at prior dose with maximized supportive care. If event occurred despite maximal supportive care, reduce pomalidomide one dose level. 	
Peripheral Neuropathy:		
Consider workup for alternative causes such as amyloidosis, diabetic neuropathy, and also neurology evaluation, since study agents uncommonly cause neuropathy. Attributing progressive neuropathy to study therapy should be done very cautiously. Study treatment should not be held for worsening peripheral neuropathy that is not due to direct neurotoxicity of therapy, especially neuropathy that precedes study participation.		
Worsening grade 2 peripheral neuropathy with pain or new grade 2-3 peripheral neuropathy	
 • Hold pomalidomide until resolution to grade ≤ 1 or to prior baseline • Reduce pomalidomide to next lower dose upon recovery 	Grade 2 signs and symptoms: Moderate symptoms; limiting instrumental activities of daily living (ADL)
New or worsening grade 4 peripheral neuropathy	
 • Discontinue pomalidomide permanently 	
Skin Rash		
Grade 2-3 non-blistering rash	
 • If offending drug is felt to be pomalidomide, hold pomalidomide and reduce to next lower dose upon return to Grade ≤ 1 or baseline. 	Maximize supportive care such as H1 and H2 blockers and/or topical corticosteroid preparations. May use short-course (< 2 weeks) oral corticosteroids if felt to be warranted.
Grade 4 non-blistering rash	
 • Discontinue offending drug permanently. 	
Grade ≥ 3 blistering / desquamating skin rash or erythema multiforme	
 • Discontinue offending drug permanently. 	

Adverse Event (Severity)	Action on Study Drugs	Further Considerations
Other grade 3 non-hematologic toxicity judged to be related to isatuximab, pomalidomide, or dexamethasone with exceptions of alopecia, electrolyte abnormalities, hyperglycemia, diarrhea, or nausea and vomiting that can be managed with supportive care and do not persist as Grade 3 toxicities for > 72 hours.	
 Hold offending drug until resolution to Grade ≤ 1 or baseline. If offending drug is pomalidomide or dexamethasone, resume at next lower dose upon return to Grade ≤ 1 or baseline. If offending drug is isatuximab, discuss resumption with study PI. 	
Other grade 4 non-hematologic toxicity	
 Permanent discontinuation of offending agent 	

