5.3 Criteria for Initiating a New Cycle of Treatment

Subject must meet the following criteria to start a cycle of treatment:

- $ANC \geq 1.0 \times 10^9/L$.*
- Platelets $\geq 50 \times 10^9/L$ if $< 50\%$ of BM nucleated cells are plasma cells.*
- Platelets $\geq 30 \times 10^9/L$ if $\geq 50\%$ of BM nucleated cells are plasma cells (cycles 1-3 only)*
- All other treatment-related, non-hematologic toxicity (except for alopecia) must have resolved to \leq Grade 1 or to the subject's baseline condition. Treatment-emergent AEs that remain above Grade 1 but are NOT felt to be related to study treatment do not require delay in study therapy, but clinician should use his/her judgment in nonetheless delaying therapy if it is in the subject's best interest clinically.

*Supportive care interventions (growth factors, transfusions, etc.) as outlined in eligibility criteria may also be employed to achieve required cell counts prior to starting a cycle of therapy.

If the subject fails to meet the above start criteria for initiation of a next cycle of treatment, dosing should be delayed for 1 week. The subject should then be re-evaluated. If the subject continues to fail to meet the above-cited criteria, delay therapy again and continue to re-evaluate weekly. For delays of >2 weeks due to cytopenias felt to be due to therapy, see Table 3 in Section 5.4.2 below.

The maximum delay before study treatment should be permanently discontinued will be 6 weeks, unless a longer delay is clinically appropriate and approved by the study PI.

See section 5.4 for dose modifications and further guidance related to dose delays.

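### Table 4 restarts pomalidomide at ANC 0.5 after each repeat grade 4 neutropenia, the same count that triggers the hold, while the general rule in the same cell requires 1.0

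*Combined protocol and SAP*

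**What the plan says.** The neutropenia row of Table 4 (section 5.4.2.2) covers mid-cycle grade 4 neutropenia, defined as ANC below 0.5 × 10⁹/L, "OR any grade febrile neutropenia". Pomalidomide is held. The general restart bullet reads "Resume pomalidomide when ANC recovers to" at least 1 × 10⁹/L "and fever and/or infections, if present, have resolved".

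The dose at that restart depends on G-CSF. It may stay the same if G-CSF is to be added and nothing else calls for a reduction. If the subject was already on the specified G-CSF, "OR investigator does not feel G-CSF is clinically appropriate, reduce pomalidomide one dose level".

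The last bullet of the cell sets a separate rule. It opens "For each subsequent drop of ANC less than" 0.5 × 10⁹/L, holds pomalidomide again, and continues: "Pomalidomide will then resume with one dose-level reduction when ANC recovers to" at least 0.5 × 10⁹/L. It does not mention fever or infection.

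Two other provisions limit where this rule operates. Section 5.3 requires ANC of at least 1.0 × 10⁹/L at the start of every cycle ("Subject must meet the following criteria to start a cycle of treatment"). Section 5.4.2.1 covers the case where the lower capsule strength cannot be supplied mid-cycle: the clinician may give the current strength every other day (option A) or leave the subject off pomalidomide until the next cycle (option B).

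**The concern.** A restart count normally sits above the hold count, so that the drug is not resumed at the edge of the event that stopped it. The general rule does this and the later-drop rule does not. The margin also runs in an unexpected direction: the subject whose marrow has already failed to tolerate the drug more than once may resume at half the count required after an initial episode.

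The population is selected for predicted high risk of severe toxicity (section 4.1.7). Section 1.7.1 cites grade 3/4 neutropenia in 85% and grade 3/4 pneumonia in 16% of patients on the same combination in the phase 3 trial. Repeat neutropenia does not by itself count toward the toxicity stopping boundary in section 10.2, which is confined to non-hematological events. Table 4 is therefore the main control on this particular toxicity.

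**Working it through.** The plan states no figure on this point that could be reproduced. The check sets the hold and restart counts side by side (all × 10⁹/L).

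| Rule in Table 4 | Hold below | Restart at or above | Restart ÷ hold | Restart − hold | Dose at restart |
|---|---|---|---|---|---|
| ANC, general rule | 0.5 | 1.0 | 1.0/0.5 = 2.0 | 0.5 | same with added G-CSF, otherwise one level lower |
| ANC, each later drop | 0.5 | 0.5 | 0.5/0.5 = 1.0 | 0 | one level lower, always |
| Platelets (context) | 25 | 50 | 50/25 = 2.0 | 25 | one level lower |

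**Does the reduction explain the lower count?** The like-for-like comparison is between a subject reduced under the general rule and a subject reduced after a later drop. Both resume one level lower, in the same cycle, after the same event. The first needs 1.0 and the second needs 0.5. The dose reduction therefore cannot by itself account for the difference.

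**Context only.** The later-drop count is 0.5/1.0 = 50% of the ANC required at entry (section 4.1.10) and at cycle start (section 5.3). The platelet row also pairs a reduction with a twofold recovery ("Resume pomalidomide with one dose level reduction only when the" count has recovered to 50). These are different decisions or a different cell line, and the conclusion does not rest on them.

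**When the rule operates.** Pomalidomide is taken on days 1 to 21. A restart at 0.5 is possible only within the cycle of the drop, by day 21, and only under option A or with the lower strength in hand. Under option B the restart waits for the next cycle, where 1.0 applies.

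**How often per subject.** Each later-drop restart uses one level of Table 3 (4, 3, 2, 1 mg, then discontinue).
- From 3 mg: 3 → 2 → 1, then stop. At most two such restarts.
- From 4 mg: 4 → 3 → 2 → 1, then stop. At most three.
- Both counts assume that the dose is not raised again after discussion with the study PI.

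**Is the dose itself too high?** No. Under option A the average daily dose is half the current strength, against the reduced level:
- 4/2 = 2.0 mg against 3 mg
- 3/2 = 1.5 mg against 2 mg
- 2/2 = 1.0 mg against 1 mg

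It never exceeds the reduced level. The issue is the count at restart.

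**The case against.** The strongest reply is that 0.5 is deliberate. The later-drop bullet pairs a lower count with a compulsory reduction, whereas the general rule can resume at full dose with G-CSF, and at 0.5 or above the subject is no longer grade 4 by the row's own definition. That trade-off is intelligible and cannot be excluded. It does not cover subjects reduced under the general rule, who still need 1.0, and the protocol does not state it.

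A reader might infer that the bullet conflicts with several thresholds across the protocol. The documents do not support that. Entry and cycle start are separate decisions that allow growth factors to reach the count, and platelet rules vary by setting: section 5.3 accepts 30 in cycles 1 to 3 when at least half of the marrow cells are plasma cells. Only the contrast within the neutropenia cell is like for like.

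A reader might also infer that pomalidomide may be resumed during an unresolved infection. That is too strong. The fever and infection clause is in the same cell, is not confined to a first event, and sits under a heading that includes febrile neutropenia, so carrying it forward is the natural reading. Table 5 separately covers drug-related grade 3 events and grade 4 events. For unrelated events, section 5.3 leaves delay of a cycle start to clinical judgment. What remains is a clarification.

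The point about reach stands. As the Time and Events Table reads, scheduled mid-cycle blood counts fall only in cycles 1 and 2 (the extracted columns may be imperfect), so many restarts would rest on counts that the clinician ordered and on the clinician's judgment.

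**Conclusion.** The inconsistency within the Table 4 neutropenia cell is real. After a repeat drop the restart count equals the hold trigger, which leaves a margin of 0 instead of 0.5 × 10⁹/L for the subjects with recurrent grade 4 neutropenia. This rests on reading the 1.0 bullet as the rule for the initial episode. The bullet does not say so, but the wording of the last bullet implies it.

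The size is modest: same-cycle restarts by day 21 only, with at most two per subject from 3 mg, or three from 4 mg, barring re-escalation. How many subjects would be affected is unknown. The 85% and 16% combine grades 3 and 4 and come from another trial, so they give no rate of repeat grade 4 drops. No endpoint, sample size or error rate changes.

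A reader might call 0.5 a typographical error. The documents do not settle that, and this point does not claim it. It is an inexpensive safety improvement to one cell.

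**What to change.** Amend the last bullet of the neutropenia row so that it reads: "Pomalidomide will then resume with one dose-level reduction when ANC recovers to" ≥ 1 × 10⁹/L "and fever and/or infections, if present, have resolved". This keeps the mandatory reduction and aligns the count and the condition with the rest of the cell.

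The cost is somewhat longer holds after repeat drops. Missed mid-cycle doses are skipped (section 5.4), so each extra day of hold within days 1 to 21 loses a dose. For a hold starting on day 10 the ceiling is 21 − 10 + 1 = 12 doses, and that includes doses missed anyway while ANC is below 0.5. G-CSF remains available to shorten the hold.

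If the sponsor confirms that 0.5 is deliberate, keep it, state the reason, and add a cross-reference to the fever and infection condition in the general bullet. That delays only subjects whose fever or infection has not resolved.

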5.4.3 Dose Modifications for Dexamethasone

For participants with contraindications to the starting dose of dexamethasone, or participants who are intolerant of the starting dose of dexamethasone due to specific toxicities attributed to dexamethasone, the dose of dexamethasone may be reduced as outlined in **Table 6**. If dose level -2 (8 mg) is not tolerated, dexamethasone should be permanently discontinued but can remain on the study with the other treatment therapies.

Table 6 Dexamethasone Dose Levels/Modifications

Dose Level	Dose (mg)
0	20 mg
-1	12 mg
-2	8 mg

5.5 Concomitant Medications/Treatments/Supportive Care Allowed, Including Required Supportive Care

The following medications and procedures are permitted during the study:

- Antiemetics, including 5-HT₃ serotonin receptor antagonists, may be used at the discretion of the investigator.
- Loperamide or other antidiarrheal agents should be used for symptomatic diarrhea at discretion of the investigator. The dose and regimen will be according to institutional guidelines. Preemptive antidiarrheals are encouraged for subjects experiencing frequent diarrhea as a result of study treatment (there is no need to wait for diarrhea to begin before initiating therapy if clinician and subject know it will occur when subject is taking,

for example, pomalidomide). Intravenous fluids should be given in cases of volume depletion.

- Growth factors (e.g., granulocyte colony stimulating factor [G-CSF], granulocyte macrophage-colony stimulating factor [GM-CSF], recombinant erythropoietin) are permitted as noted elsewhere in this protocol. Their use should follow published guidelines and/or institutional practice.
- Subjects should be transfused with red blood cells and platelets as clinically indicated and according to institutional guidelines.
- Prophylactic antiviral therapy with acyclovir, valacyclovir, or similar agent is required unless a compelling contraindication exists.
- Prophylactic antibiotics are permitted per local institutional guidance, especially among participants with Grade 3-4 neutropenia.
- Concomitant treatment with bisphosphonates or denosumab is allowed if the patient has previously received dental clearance to minimize risk of osteonecrosis of the jaw.
- Venous thromboembolic event (VTE) prophylaxis is strongly encouraged with aspirin (dose determined by treating clinician) or any form of anticoagulation, depending on VTE risk as assessed by treating clinician.
- HBV vaccination may be considered, following the investigator's discretion, for patients with negative HBsAg, total anti-HBc, anti-HBs and HBV-DNA. In case of viral reactivation during study treatment, study treatment should be held, and specialist may be consulted for initiation of anti-viral treatment and monitoring of the patient. Re-initiation of study treatment may be considered at the discretion of the treating clinician only if specialist (hepatologist) is in agreement (if consulted) and only if infection is acceptably controlled. Close monitoring of ALT and AST should then be continued up until study treatment discontinuation and HBV DNA to be monitored as per specialist advice.

5.6 Contraceptive Requirements

FCBP or male subjects with female partners of childbearing potential shall be required agree to practice true abstinence, when this is in line with the preferred and usual lifestyle of the subject or to use contraception as outlined below.

- FCBP must agree to initiate and practice contraception (using 2 effective methods – 1 highly effective method (Section 5.6.1.1) and 1 additionally effective method (Section 5.6.1.2) at the same time) at least 28 days before starting pomalidomide treatment through 90 days after the last dose of pomalidomide or 5 months after the last dose of isatuximab.
- Male subjects with female partners of childbearing potential, even if surgically sterilized (i.e., status post vasectomy) must agree to use barrier contraception (latex or synthetic condom) 2 weeks prior to study drug administration, during

the entire study treatment period and through 90 days or 5 months after the last dose of pomalidomide or isatuximab, respectively.

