4.1.11 Male or Female Contraceptive Requirements

a) Male participants

Men must agree to use a latex or synthetic condom during sexual contact with a FCBP even if they have had a vasectomy from the time of signing the informed consent form through 90 days after the last dose of pomalidomide and 5 months after the last dose of isatuximab. These same patients must not donate sperm.

b) Female participants

A female participant is eligible to participate if she is not pregnant, not breastfeeding, and at least one of the following conditions applies:

Not a Female of childbearing potential (FCBP)*,

OR

If an FCBP, participant must have a negative serum or urine pregnancy test with a sensitivity of at least 25 mIU/mL within 10 – 14 days prior to and again within 24 hours of starting pomalidomide and must either commit to continued abstinence from heterosexual intercourse or begin TWO acceptable methods of birth control, one highly effective method and one additional effective method AT THE SAME TIME (Male or Female Contraceptive Requirements), at least 28 days before she starts taking pomalidomide through 90 days after the last dose of pomalidomide and 5 months after the last dose of isatuximab. FCBP must also agree to ongoing pregnancy testing during the entire duration of treatment and monthly for 5 months after the last dose of isatuximab. All patients must be counseled at a minimum of every 28 days about pregnancy precautions and risks of fetal exposure. All patients enrolled into this trial, must be registered in and must comply with all requirements of the POMALYST REMS program.

*A female of childbearing potential (FCBP) is a sexually mature female who: 1) has not undergone a hysterectomy or bilateral oophorectomy; or 2) has not been naturally postmenopausal for at least 24 consecutive months (i.e., has had menses at any time in the preceding 24 consecutive months).

4.1.12 Subject may be HIV+ if the following criterion are met:

1. CD4+ T-cell counts ≥ 350 cells/ μ L
2. No history of AIDS-defining opportunistic infections
3. Subject is on an established antiretroviral therapy (ART) for at least 4 weeks prior to initiation of study treatment.
4. Absence of known, clinically significant drug-drug interactions with isatuximab, pomalidomide, and dexamethasone.

4.1.13 Subjects is willing and able to comply with study procedures based on the judgement of the investigator or protocol designee.

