5.4.2 Pomalidomide Dose Modifications/Delays

Allowable dose adjustments/reductions are outlined in Table 3. If 1 mg is not tolerated despite maximal supportive care, then pomalidomide should be permanently discontinued and other study drugs may be continued if felt to be appropriate by the treating clinician.

Table 3 Pomalidomide Dose Levels/Modifications

Dose Level	Dose (mg)
+1*	4 mg
0	3 mg
-1	2 mg
-2	1 mg
-3	Discontinue

**If after 3-cycles, the patient has SD (<MR) and has not experienced any grade ≥ 3 hematologic toxicities or treatment-related grade ≥ 2 non-hematologic toxicities, at the investigator's discretion, the dose of pomalidomide may be increased to 4 mg beginning*

with cycle 4. Pomalidomide dose increases to 4 mg may also be considered in other situations on a case-by-case basis after discussion with the PI.

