6.1.5 Managing Infusion Reactions

Table 8 Infusion Reaction Management

Severity (CTCAE version 5.0)	Recommendation intervention
Mild (Grade 1) Infusion interruption or intervention not indicated	Continuation of isatuximab infusion per the judgment of the Investigator following close direct monitoring of the patient's clinical status. Isatuximab infusion may be stopped at any time if deemed necessary. If stopped, IR will be classified as Grade 2 as per NCI-CTCAE and infusion will be restarted at half of the initial infusion rate.
Moderate (Grade 2) Therapy or infusion interruption indicated but responds promptly to symptomatic treatment (e.g., antihistamines, NSAIDs, narcotics, IV fluids); prophylactic medications indicated for ≤ 24 hours	Stop isatuximab infusion. Give additional medication with IV diphenhydramine 25 mg IV (or equivalent) and/ or IV methylprednisolone 100 mg (or equivalent) as needed. Isatuximab may be resumed only after patient recovery, at half the infusion rate and with close monitoring.

Severe or life-threatening (Grade 3 or 4)
 
Grade 3: prolonged (e.g., not rapidly responsive to symptomatic medication and/or brief interruption of infusion); recurrence of symptoms following initial improvement; hospitalization indicated for clinical sequelae
 
Grade 4: life-threatening consequences; urgent intervention indicated.
	
Stop the isatuximab infusion. Give additional medication with diphenhydramine 25 mg IV (or equivalent) and/or IV methylprednisolone 100 mg (or equivalent) and/or epinephrine as needed until the resolution of the AE or until the AE improves to Grade 1. Only then, if previous Grade 3 the infusion may be restarted at the Investigator's discretion; if so, the infusion rate should be half of the infusion rate before the interruption, and it may be increased subsequently, at the Investigator's discretion. If the severity of an infusion-related AE returns to Grade 3 after the restart of the infusion, the same procedure described above may be repeated at the Investigator's discretion. If a Grade 3 infusion-related AE occurs for a 3rd time, treatment with isatuximab will be definitively discontinued for that participant.
 
In case of Grade 4, isatuximab will be permanently discontinued.

--	--

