6.1.12.3 Reproductive toxicity, pregnancy and breast feeding

The effects of isatuximab on reproductive toxicity, pregnancy and lactation have not been investigated in formal toxicity studies. Therefore, the effects of isatuximab on reproductive organs in males and females are unknown.

Females of childbearing potential or male subjects with female partners of childbearing potential shall be required to use highly effective contraceptive methods (a failure of <1% per year when used consistently and correctly) starting 28 days before first isatuximab administration, while on therapy and for 5 months following the last dose of isatuximab. A woman is considered of childbearing potential, i.e., fertile, following menarche and until becoming post-

menopausal unless permanently sterile. The following highly effective methods of contraception are accepted:

- Established use of oral, intravaginal, or transdermal combined (estrogen and progestogen
- containing) hormonal contraception associated with inhibition of ovulation
- Established use of oral, injectable, or implantable progestogen-only hormonal
- contraception associated with inhibition of ovulation
- Placement of an intrauterine device or intrauterine hormone-releasing system
- Bilateral tubal occlusion
- Male sterilization (provided that the partner is the sole sexual partner of the patient and
- that the sterilized partner has received medical assessment of the surgical success)
 - Sexual abstinence during the entire period of risk associated with study treatments. If a woman becomes pregnant while taking isatuximab, treatment with isatuximab should be discontinued and the pregnancy should be followed until its outcome.

For complete guidance, please refer to the Guidance on Pregnancy and Contraception in the study protocols.

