7.3.3 Pregnancy Test

Frequent pregnancy testing is required for females of childbearing potential who receive pomalidomide. See the **Time and Events Table**.

Because of the embryo-fetal risk, POMALYST is available only through a restricted program under a Risk Evaluation and Mitigation Strategy (REMS) called “**POMALYST REMS.**”

Required components of the **POMALYST REMS** program include the following:

- Prescribers must be certified with the **POMALYST REMS** program by enrolling and complying with the REMS requirements.
- Patients must sign a Patient-Physician Agreement Form and comply with the REMS requirements. In particular, female patients of reproductive potential who are not pregnant must comply with the pregnancy testing and contraception requirements and males must comply with contraception requirements.
- Pharmacies must be certified with the **POMALYST REMS** program, must only dispense to patients who are authorized to receive POMALYST, and comply with REMS requirements.

Further information about the **POMALYST REMS** program is available at www.CelgeneRiskManagement.com or by telephone at [name].

If a woman becomes pregnant while taking isatuximab, treatment with isatuximab should be discontinued and the pregnancy should be followed until its outcome.

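### Section 5.6 joins the two post-treatment contraception windows for female subjects of childbearing potential with 'or', in conflict with 4.1.11(b) and 6.1.12.3, which require the full isatuximab window

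*Combined protocol and SAP*

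**What the plan says.** Three places in the protocol state when an FCBP may stop contraception.

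- **Section 5.6, FCBP bullet:** "through 90 days after the last dose of pomalidomide or 5 months after the last dose of isatuximab". The bullet contains neither 'respectively' nor 'whichever is later'.
- **Section 4.1.11(b), inclusion criterion:** contraception is to begin four weeks or more "before she starts taking pomalidomide through 90 days after the last dose of pomalidomide and 5 months after the last dose of isatuximab". The same criterion requires pregnancy testing throughout treatment and then every month for 5 months after isatuximab ends.
- **Section 6.1.12.3, isatuximab drug information:** contraception is required "starting 28 days before first isatuximab administration, while on therapy and for 5 months following the last dose of isatuximab".

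Two other provisions bear on the point. The male bullet in 5.6, directly below the FCBP bullet, uses the same two windows but ties each to its own drug with 'respectively'. Section 5.4.2 lets the two drugs stop at different times: if the lowest dose is not tolerated, "pomalidomide should be permanently discontinued and other study drugs may be continued".

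**The concern.** Section 5.6 is the protocol's dedicated contraception section, so it is a natural place for site staff to look. Two alternatives joined by a bare 'or' are met once either one is met, so a literal reader could stop at the earlier date. The other two sections require the later one.

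The stake is fetal exposure. Section 6.1.12.3 says the effects of isatuximab on the reproductive organs are unknown. For pomalidomide, section 7.3.3 states: "Because of the embryo-fetal risk, POMALYST is available only through a restricted program". The disputed interval also falls mostly after treatment, when scheduled contact thins out: the pregnancy-test and contraception row of the Time and Events Table (section 8.1) has no entry after the end-of-treatment visit.

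**Working it through.** The plan states no figure to reproduce. The check compares the stop dates under the two wordings.

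**Inputs**
- Pomalidomide window: 90 days (5.6, 4.1.11(b)).
- Isatuximab window: 5 months (5.6, 4.1.11(b), 6.1.12.3). Counted from every start date in 2024 to 2027, 5 calendar months are 150 to 153 days.
- Schedule (5.2): pomalidomide on days 1 to 21 of each cycle. Isatuximab on days 1, 8, 15 and 22 of cycle 1, then days 1 and 15.

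**Formula**
Let G be the day of the last isatuximab dose minus the day of the last pomalidomide dose. Counted from the last pomalidomide dose, the pomalidomide window ends at day 90 and the isatuximab window at day G + 150 to G + 153. The wording of 4.1.11(b) requires the later end; a literal 'or' allows the earlier. When the isatuximab window ends later, the shortfall is (G + 150 to 153) − 90 = G + 60 to G + 63 days.

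**Results**

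| Situation | G | Shortfall against the isatuximab window (days) |
|---|---|---|
| Both drugs stop on the same day | 0 | 60 to 63 |
| Completed cycle from cycle 2 on (isatuximab day 15, pomalidomide day 21) | 15 − 21 = −6 | 54 to 57 |
| Completed cycle 1 only (isatuximab day 22, pomalidomide day 21) | 22 − 21 = 1 | 61 to 64 |
| Pomalidomide stops 28 days before isatuximab | 28 | 88 to 91 |
| Pomalidomide stops 90 days before isatuximab | 90 | 150 to 153 (the whole window) |

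For G above 90, the literal stop date falls G − 90 days before the last isatuximab dose, so contraception could end during isatuximab treatment. That contradicts the on-therapy requirement in 6.1.12.3. Section 5.4.2 makes this sequence possible, because it allows the other drugs to continue after pomalidomide is stopped.

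With 'and' and 'whichever is later', the shortfall is zero in every row.

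**The case against.** The strongest reply is that 5.6 says what an FCBP must agree to and releases her from nothing else. The rules are cumulative: anyone who meets 4.1.11(b) also meets 5.6. The full window is an entry commitment, and 11.5.2 rules out eligibility exceptions. Monthly pregnancy testing for 5 months after isatuximab spans the interval in question. Registration in the pomalidomide REMS program and counselling at least every 28 days are mandatory. The literal reading is also implausible, since it can end contraception during treatment. The male bullet shows the intended meaning, and 5.6.1.1 defines abstinence as covering the whole period of risk.

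Most of this stands. A reader might infer that the protocol as a whole lets an FCBP stop early. It does not, because 4.1.11(b) and 6.1.12.3 still bind. What remains is that the safeguards do not correct the sentence in 5.6. Pregnancy testing detects a pregnancy but does not prevent one. No text ranks 4.1.11(b) above 5.6, and 6.1.12.3 closes by sending the reader to the protocol's contraception guidance, which could lead back to 5.6.

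Two further readings are tempting and should not be adopted.

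- **That the pomalidomide window can equally be cut short.** This would need pomalidomide to continue well after isatuximab stops. The protocol provides for stopping isatuximab ("In case of Grade 4, isatuximab will be permanently discontinued" in 6.1.5; "Permanent discontinuation of offending agent" in Table 5) but does not state that pomalidomide then continues. For an assumed gap of 84 days, the isatuximab window would end at day 150 − 84 = 66 to 153 − 84 = 69 after the last pomalidomide dose, 21 to 24 days short of 90. That figure rests wholly on the assumption.
- **That the differing male start times need the same correction.** They do differ: signing of consent (4.1.11(a) and footnote 1e of 8.1), 2 weeks before study drug (5.6), and 28 days before isatuximab (6.1.12.3, which also covers men: "male subjects with female partners of childbearing potential shall be required to use highly effective contraceptive methods"). The 5.6 and 6.1.12.3 starts precede dosing, as does consent, and 6.1.12.3 defers to the protocol's guidance. Replacing the fixed 2-week lead with the consent date could shorten protection when consent is signed later than day −14.

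**Conclusion.** The FCBP stop rule in 5.6 conflicts with 4.1.11(b) and 6.1.12.3 and should be corrected. Under the literal reading, the size is about two months of the isatuximab window in ordinary stopping patterns, and more if pomalidomide stops first. These counts assume that a site follows 5.6 alone and takes 'or' at face value; reading it as one window per drug gives the right rule and no shortfall.

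It is probably a drafting slip. Few FCBP can be expected in a trial aimed at elderly or frail subjects, and the consent text, which could confirm or correct the instruction given to subjects, is not available for review. No endpoint, sample size or analysis is affected. The case for acting is that a safety rule is worded wrongly and costs almost nothing to put right.

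**What to change.** In the FCBP bullet of 5.6, replace the 'or' between the two windows with 'and', and add 'whichever is later' at the end, so that the bullet agrees with 4.1.11(b). Check that the consent form gives the same stop rule. Leave the male bullet of 5.6 and the male start times as they are.

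The cost is one reworded bullet at the next amendment plus the consent check. Design, sample size and analysis do not change.
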